Patients will provide appropriately-obtained informed consent prior to initiating any screening procedures. Patients meeting initial screening criteria will be eligible to continue to the Day 1 visit for review of eligibility and baseline assessments, including SALT assessment, physical examination, clinical laboratory assessments, and vital signs. Patients meeting all inclusion criteria and none of the exclusion criteria will be randomized to twice-daily treatment with either 12 mg CTP-543, 8 mg CTP-543 or placebo. Patients will be randomized in a 1:2:1 ratio (12 mg BID:8 mg BID:placebo). Randomization will be stratified by scalp hair loss into one of the following two categories: 1) Partial scalp hair loss (SALT  $\geq$  50 and < 95); 2) complete or near-complete scalp hair loss (SALT  $\geq$  95). Patients will take the first dose of study drug in the clinic on Day 1 and will be instructed to take study drug daily approximately every 12 hours for the duration of the Treatment Period. Patients should dose study drug in the clinic on all Study Visit Days after clinical laboratory blood draws are completed. Other baseline assessments will include patient and clinician global impression of disease severity (CGI-S and PGI-S), Patient Reported Outcome for Satisfaction (SPRO) and Hair Quality (QPRO), the Hospital Anxiety and Depression Scale (HADS), and assessments for eyelash and eyebrow involvement.

The double-blind, placebo-controlled Treatment Period will last 24 weeks. Assessment of treatment response using SALT for efficacy will occur at 4, 8, 12, 16, 20 and 24 weeks.

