| HBV and HCV test  | X   |                              |                               |                                  |    |                          |                                    |
| 12-lead electrocardiogram   | X   |                              |                               | $X^{12}$                         |    | X                        |                                    |
| Vital signs   | X   | X                            |                               | X                                | X  | X                        | X                                  |
| Severity of Alopecia Tool assessment                                   | X   | X                            |                               | X                                | X  | X                        |                                    |
| Photographs of the scalp  | X   | X                            |                               | X                                | X  | X                        |                                    |
| Photographs of eyebrows, eyelashes, and hands                                       |   | X                            |                               | X                   |    | X                        |                                    |
| Eyebrow Assessment (BETA)   |   | X                            |                               | X                   |    | X                        |                                    |
| Eyelash Assessment (BELA)   |   | X                            |                               | X                   |    | X                        |                                    |
| Patient Reported Outcome Scales: SPRO and QPRO                                      |   | X                            |                               | X                   | X  | X                        |                                    |
| Patient and Clinical Global Impression of Improvement (PGI-I, CGI-I  ) |   |                              |                               | X                   | X  | X                        |                                    |
| Patient and Clinical Global Impression of Severity (PGI-S, CGI-S  )    |   | X                            |                               | X                   | X  | X                        |                                    |

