## HBV = hepatitis B virus; HCV = hepatitis C virus

 Due to the COVID-19 pandemic, patient study visits may be performed remotely when the provider and patient are not able to be physically present in the clinic. Study personnel should strive to perform assessments per the schedule of events above with the understanding that all assessments may not be able to be performed (ECGs, vitals, SALT assessments).

-  Randomization/Day 1 may occur any time after eligibility has been confirmed.
- $^3$  All subsequent visits and week increments should be based on the date of Visit 2 (Day 1).  $^4$  All visit windows are  $\pm 2$  days.
-  The Safety Follow-Up Visit is intended for those patients who do not roll over into the Open-Label Extension.

 For females of childbearing potential, a serum pregnancy test will be performed at Screening. Throughout the Treatment Period, and at the safety follow-up (if applicable), urine pregnancy tests will be performed.

 Includes fasted hematology, serum chemistry, and lipids performed by the central lab.

8 Collected pre-dose.

-  Will include thyroid stimulating hormone and hemoglobin A1c at Screening only.
-  Will include hematology and serum chemistry **only**.
-  Should be performed by the same rater for the patient for the duration of the study.
-  Performed at Week 12 only.
-  Due to COVID-19, Site to Subject (STS) or Direct to Subject (DTS) shipping services may be warranted in cases where a patient is not able to attend in clinic visits or a site is closed.
-  Collection is ongoing.

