#### 8.1.4. Multiple Comparisons/Multiplicity

Hierarchical testing will be used to control for multiple comparisons (Figure 1). For the primary efficacy analysis and the key secondary efficacy analyses, a  $\leq 0.025$  (two-sided) alpha-level will be allocated to each dose for comparison with placebo to adjust for multiplicity of testing associated with two doses. Once p>0.025 is observed for a treatment group comparison, inference for additional endpoints is no longer alpha-level protected for that dose group, however nominal p-values will still be reported.

Subsequently, conditional upon significance ( $\leq 0.025$ ) for the primary endpoint and first key secondary endpoint for each dose, a linear hierarchical testing approach with  $\leq 0.025$  (two-sided) alpha-level will be used to test the remaining key secondary endpoint comparisons versus placebo. Once p>0.025 is observed for a treatment group comparison, inference for additional endpoints is no longer alpha-level protected for that dose group; however, nominal p-values will still be reported.

All other statistical tests outside of the hierarchy will be carried out at a two-sided significance level of  $\leq 0.05$ . Nominal p-values will be presented without adjustment for multiple comparisons.

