#### 8.2.1. Computation of the Primary Endpoint

The SALT is a measure of hair loss that quantifies the amount of scalp surface without hair in a pre-specified quadrant of the scalp (right side, top, left side, back), that is further summed after applying a quadrant-specific multiplier indicative of scalp surface area contribution, to provide an overall score of total hair loss. A total SALT score equal to 0% indicates complete hair growth. A total SALT score equal to 100% indicates complete hair loss. An example of the SALT assessment can be found in Appendix 17.2 of protocol. The overall total SALT score is calculated in the eCOA system and will not re-derived. SALT scores are considered missing if the overall total could not be calculated. The primary endpoint is derived by categorizing the individual overall SALT scores at Week 24 ( $\leq 20$  versus > 20).

A multiple imputation (MI) approach will be used to estimate missing SALT scores.

One hundred independent imputations will be done with SAS® PROC MI using the Fully Conditional Specification (FCS) regression method. The FCS method combines both the monotone and arbitrary missing data patterns into one procedure, imputing missing values with a sequential regression approach.

For the primary efficacy analysis, missing SALT scores will be imputed under a missing at random (MAR) assumption. This assumes that patients who have missing data would have similar SALT scores as other patients in their respective treatment arm who have complete data. Any missing post-baseline SALT scores will be imputed to better inform the estimates of Week 24 missing SALT scores. Patients who have discontinued treatment but remain on study will not have their SALT scores censored, but any arbitrary missing SALT scores after the patient discontinued treatment will be imputed in the same manner. Utilizing the FCS method, missing

SALT scores will be imputed in a sequential manner using regression models with baseline SALT score and the observed or imputed values of previous visits as covariates. Imputations will be implemented separately for each treatment under the assumption that different treatments may have distinct posterior distributions.

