#### **Figure 1: Hierarchical Testing**

#### 8.3.1. Satisfaction of Hair Patient Reported Outcome (SPRO) at Week 24

The first key secondary endpoint is the percentage of responders per the SPRO at Week 24. The SPRO is a single item questionnaire answered by the patient, designed to measure how satisfied alopecia areata patients are with their hair at the time of the assessment. The SPRO responses are on a scale of 1-5, where 1 = very satisfied, 2 = satisfied, 3 = neither satisfied nor dissatisfied, 4 = dissatisfied, and 5 = very dissatisfied. An example of the SPRO assessment can be found in Appendix 17.4.1 of the protocol.

A responder is defined as patients with answers of "very satisfied" or "satisfied" at Week 24 on the SPRO. This endpoint will be assessed similar to the primary analysis of the primary endpoint, according to Section 8.2.2.

Missing data will be imputed similarly to the primary endpoint according to Section 8.2.1. However, since the SPRO scale is ordinal, the FCS logistic regression method will be used in lieu of the FCS regression method. The missing SPRO scores will be imputed in a sequential manner using logistic regression models with baseline SALT score, baseline SPRO score, and the observed or imputed SPRO values of previous visits as covariates.

The observed number and percentage of SPRO responders by treatment group will be reported along with the appropriate p-values. Both CTP-543 doses will be tested in parallel against placebo with a  $\leq 0.025$  alpha level. This analysis will be completed for the Efficacy Population, the Per Protocol Population, and the Modified Efficacy Population. The Per Protocol Population will be considered supportive. The analysis utilizing the Modified Efficacy Population is considered a sensitivity analysis. If the primary endpoint is unsuccessful, nominal p-values will be reported.

#### 8.3.2. SALT Score ≤ 20 at Weeks 20, 16, 12, and 8

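### The SPRO imputation model ignores Week 4 and Week 8 SALT, so patients who leave the study before Week 12 are imputed from baseline data within arm; any resulting bias is conditional and small, and cheap to reduce.

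*SAP*

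**What the plan says.** SAP 8.3.1 makes the proportion of SPRO responders at Week 24 the first key secondary endpoint. Missing scores are imputed along the lines of SAP 8.2.1, with one change of method: "the FCS logistic regression method will be used in lieu of the FCS regression method". The covariates are "baseline SALT score, baseline SPRO score, and the observed or imputed SPRO values of previous visits as covariates". SAP 8.2.1 also fixes that "Imputations will be implemented separately for each treatment under the assumption that different treatments may have distinct posterior distributions".

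The two instruments follow different schedules. For SALT, the protocol synopsis states: "Assessment of treatment response using SALT for efficacy will occur at 4, 8, 12, 16, 20 and 24 weeks". In Protocol Table 2 the row "Patient Reported Outcome Scales: SPRO and QPRO" has an entry in the combined Week 4, 8 and 12 column, but its footnote reads "Performed at Week 12 only". SPRO is thus collected at baseline and at Weeks 12, 16, 20 and 24.

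The primary endpoint is treated differently. SAP 8.2.1 says: "Any missing post-baseline SALT scores will be imputed to better inform the estimates of Week 24 missing SALT scores". Early SALT therefore informs imputed Week 24 SALT.

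On testing, SAP 8.1.4 makes the remaining key secondary tests (SALT of 20 or less at Weeks 20, 16, 12 and 8) conditional on significance "for the primary endpoint and first key secondary endpoint for each dose, a linear hierarchical testing approach". The missing-not-at-random and tipping-point analyses in SAP 8.2.3 cover the primary endpoint only. SPRO is repeated in the Per Protocol and Modified Efficacy Populations.

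**The concern.** Missing at random is an assumption about a particular imputation model: given the variables in that model, missingness must not depend on the unseen outcome. A patient who leaves after Week 8 and before Week 12 may have two observed post-baseline SALT scores and no post-baseline SPRO. For that patient the earlier SPRO values named in the covariate list are themselves imputed from the baseline scores, so they add no information. If such patients leave because their hair is not regrowing, the model cannot see it and gives them roughly the response rate of similar patients who stayed.

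SAP Section 13 says SPRO imputation was added so that missing data would be handled in line with the other alpha-controlled endpoints. The covariate list falls short of that aim: the SALT endpoints use early regrowth and SPRO does not. Section 13 explains the move to the logistic method but not the choice of covariates.

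At stake is the estimate for an endpoint that gates four further tests per dose. The planned SPRO repeats change the population, not the missing-data assumption, so they would not reveal the problem.

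**Working it through.** **1. The plan's own figure.** The documents give no power or missing-data figure for SPRO. The nearest is the primary-endpoint power in Protocol 12.1: response rates 40%, 26% and 9%; 110, 220 and 110 patients (12 mg, 8 mg, placebo); continuity-corrected chi-square; two-sided 0.025. With the pooled standard error under the null (SE0), the unpooled one under the alternative (SE1), correction c = 0.5 × (1/n1 + 1/n0) and z = 2.2414,

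power = Φ[(p1 − p0 − c − z × SE0) / SE1].

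- 12 mg: (0.31 − 0.0091 − 2.2414 × 0.0580) / 0.0541 = 3.16, power 99.9% (stated: above 99%).
- 8 mg: (0.17 − 0.0068 − 2.2414 × 0.0470) / 0.0402 = 1.44, power 92.5% (stated: about 92%).

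Both figures reproduce. SE1, 5.4 points for 12 mg and 4.0 for 8 mg, is the yardstick below.

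**2. What the SPRO model can use, by time of leaving the study.**

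| Last visit attended | Post-baseline SALT observed | Post-baseline SPRO observed | Used in the SPRO model |
|---|---|---|---|
| Week 4 | Week 4 | none | baseline SALT, baseline SPRO |
| Week 8 | Weeks 4, 8 | none | baseline SALT, baseline SPRO |
| Week 12 or later | Weeks 4, 8, 12 onward | Week 12 onward | baseline scores and observed SPRO |

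The full loss of post-baseline information is confined to the first two rows (assuming no missed assessments).

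**3. Size, on assumed inputs.** The assumptions are:

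- Week 24 SPRO response of 40%, 26% and 9%, borrowed from the SALT assumptions because no SPRO rates are given.
- A proportion d of 2%, 5% or 10% leaving before Week 12 in every arm.
- Odds of leaving multiplied by 1, 2 or 3 per standard deviation less early regrowth.
- A latent correlation of 0.3, 0.5 or 0.7 between early SALT change and Week 24 SPRO.
- Baseline-only imputation gives leavers the stayers' response rate in their arm.

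With true rate p in the whole arm and pL among leavers,

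stayers' rate = (p − d × pL) / (1 − d); bias in the arm = stayers' rate − p.

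The bias in the risk difference is the active-arm bias minus the placebo bias. In the worst setting (d = 10%, odds ratio 3, correlation 0.7), pL is 18.4%, 9.7% and 2.2%:

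- 12 mg: (0.40 − 0.0184) / 0.90 = 0.424, bias +2.4 points.
- 8 mg: (0.26 − 0.0097) / 0.90 = 0.278, bias +1.8 points.
- Placebo: (0.09 − 0.0022) / 0.90 = 0.0976, bias +0.75 points.
- Risk difference: 2.40 − 0.75 = 1.65 points (12 mg); 1.81 − 0.75 = 1.06 points (8 mg).

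Overstatement of the risk difference across all settings, in percentage points:

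| Leaving before Week 12 | Odds ratio 1 | 12 mg, odds ratio 2 to 3 | 8 mg, odds ratio 2 to 3 |
|---|---|---|---|
| 2% | 0.0 | 0.1 to 0.3 | 0.1 to 0.2 |
| 5% | 0.0 | 0.2 to 0.8 | 0.2 to 0.5 |
| 10% | 0.0 | 0.5 to 1.7 | 0.3 to 1.1 |

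Against the standard errors, the worst cases are 1.65 / 5.4 = 0.3 (12 mg) and 1.06 / 4.0 = 0.3 (8 mg). At 5% leaving, the 12 mg worst case is 0.84 / 5.4 = 0.16. If leaving depends only on early SALT, a model that includes early SALT removes the bias.

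**The case against.** The other side has a good deal to say.

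- **The affected group may be small.** Protocol 8.3 keeps patients who stop study drug in follow-up with all endpoints collected. Protocol 10.5 has SPRO done by video when COVID-19 prevents a clinic visit, whereas Protocol 10.2 says SALT is then not done. Only study withdrawal or missed assessments leave SPRO missing. At 2% to 10%, early leavers would be about 2 to 11 of 110 patients. This stands.
- **Placebo is biased the same way.** The tested quantity is the risk difference, so part of the arm-level bias cancels. If a dose had no effect and patients left alike in both arms, all of it would cancel. This stands; a reader might infer a false-positive gate, but the documents do not support that.
- **Early SALT may predict little.** Protocol 4.4.2 reports significant separation from placebo in Phase 2 from about Week 12, so slow regrowth at Week 8 need not mean non-response at Week 24. This is why correlations down to 0.3 were used.
- **A short covariate list protects stability.** Up to six correlated SALT scores in an arm-specific five-level ordinal model, with perhaps 10 placebo responders (9% of 110), could fail to fit. This stands against adding every visit, but not against one or two terms.

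It is also tempting to say that the protocol already brings SALT in, because Protocol 12.4.5 uses all other continuous variables when imputing classification variables. That does not settle it: the protocol did not impute non-SALT endpoints, the SAP gives an explicit list, and SAP Section 2 gives the SAP precedence.

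**Conclusion.** The gap in the covariate list is a matter of text and is certain. Its effect is conditional. The SPRO risk difference is overstated only if withdrawal before Week 12 depends on early regrowth beyond what arm and baseline scores explain. On the assumed inputs the overstatement is about 0.1 to 0.8 points at 2% to 5% early withdrawal and at most about 1.7 points at 10%, against a standard error of 4 to 5 points. It is zero if withdrawal is unrelated to early SALT.

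A reader might infer that SPRO imputations are too optimistic whatever the reason for leaving, or that everyone who stops treatment is affected. The documents support neither. Withdrawal for adverse events or logistics need not follow regrowth; patients who only stop drug are still assessed; and those who leave after Week 12 normally have an observed SPRO in the model. No wrong conclusion at the gate has been shown.

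This is a modest weakness worth correcting because the endpoint is a gate, its missing-data assumption is not stress-tested, and the needed data are already collected and imputed. The size rests on borrowed response rates and assumed withdrawal rates and correlations.

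**What to change.** Before unblinding, amend SAP 8.3.1 so that SALT is imputed first, as already planned, and a small number of post-baseline SALT terms enter the SPRO imputation model as continuous covariates. Week 8 SALT, or SALT at the visit being imputed, would serve. State a fallback to the current list if an arm-specific ordinal model does not converge, and record the change in SAP Section 13. If the blind has already been broken, report the extended model as a sensitivity analysis.

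The cost is a sentence or two in the SAP and one or two more parameters per arm-specific model. A small simulation at 110, 220 and 110 patients (40 runs per setting) with one early SALT term reduced the bias in every arm, with no fitting failures and no loss of precision. Forty runs cannot exclude rare failures, hence the fallback.

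The extended model still assumes missing at random. A tipping-point or missing-not-at-random analysis for SPRO at Week 24, modelled on SAP 8.2.3, would cover what it cannot.

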#### 8.4. Secondary Endpoints

All statistical tests outside of the hierarchy defined in Section 8.1.4 and Section 8.3 will be carried out at a two-sided significance level of  $\leq 0.05$ . Nominal p-values will be presented. Analyses will be performed using the Efficacy Population.

Missing values will not be imputed for efficacy endpoints that are not derived from SALT or SPRO scores.

For the secondary endpoints of proportions of patients achieving specified improvement criteria (hereinafter, "secondary responder endpoints"), pairwise treatment group differences from placebo at each scheduled evaluation will be assessed with the Cochran-Mantel-Haenszel test using baseline scalp hair loss as the stratification factor. Observed counts and percentages of responders will be summarized by treatment group and the p-values reported. Secondary responder endpoints derived from SALT or SPRO scores will be analyzed similarly to the primary endpoint according to Section 8.2.2.

For the secondary endpoints of absolute or relative changes (hereinafter, "continuous secondary endpoints"), treatment differences will be assessed with a mixed-effect model of repeated measures (MMRM). Model covariates are described in applicable sections below. Treatment group comparisons at each visit will be based on least squares (LS) mean estimates. An unstructured covariance matrix will be used to model the within-subject errors. Should the model fail to converge, an alternative autoregressive covariance matrix will be used instead. The Kenward-Roger approximation will be used to estimate the denominator degrees of freedom. Assuming that the data are MAR, the estimates of the treatment differences calculated from the

MMRM described above are unbiased. Standard descriptive statistics will be reported for each time point on the values and changes from baseline along with the LS means, standard errors, 95% CIs and differences between treatment groups reported with LS means, standard errors, and 95% CIs.

#### 8.4.1. Secondary SALT Endpoints

The following secondary SALT responder endpoints will be assessed:

- Percentage of patients achieving at least a 75% relative reduction in SALT score from Baseline at Weeks 12 and 24
- Percentage of patients achieving at least a 90% relative reduction in SALT score from Baseline at Weeks 12 and 24
- Percentage of patients achieving an absolute SALT score of  $\leq 20$  at Week 4
- Percentage of patients achieving an absolute SALT score of  $\leq 10$  at Week 24

In addition, the continuous secondary SALT endpoint of relative change in SALT score from baseline at Weeks 4, 8, 12, 16, 20, and 24 will be assessed with a MMRM. The model will include fixed factors for treatment group, study visit, and treatment by study visit interaction, with baseline SALT score as a covariate. Imputed values will not be used for the MMRM.

Relative reduction is based on relative change from baseline.

Relative change in SALT score is derived as percent change of the follow-up SALT score, where baseline SALT score is the denominator (i.e. absolute change divided by the baseline score, multiplied by 100).

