## 4.4.2. Clinical Studies of CTP-543 in Patients with Alopecia Areata

Three Phase 2 studies in patients with moderate to severe AA have been completed and one Phase 2 trial is currently ongoing. An Open-Label Extension study (CP543.5001) and a Phase 3 study (CP543.3001) are currently ongoing.

Study CP543.3001 is a double-blind, randomized, placebo-controlled trial in 700 patients with moderate to severe alopecia areata being conducted in the US, Canada, and select EU countries. For more details of these studies, please see the CTP-543 Investigator's Brochure.

Study CP543.2001 was a double-blind, randomized, placebo-controlled Phase 2 dose ranging study to evaluate the safety and efficacy of CTP-543 in adult patients with moderate to severe alopecia areata. A total of 149 adults with moderate to severe alopecia areata were enrolled CONFIDENTIAL & PROPRIETARY

across three cohorts. Patients were sequentially randomized to receive one of three doses of CTP-543 (4, 8, 12 mg twice daily) or placebo for 24 weeks.

The overall objectives of the study were to assess the safety and efficacy of a 24-week regimen of administration of 4, 8, or 12 mg BID CTP-543 compared with matching placebo in adult patients with moderate to severe alopecia areata. The primary efficacy endpoint was the proportion of responders, defined as patients achieving at least a 50% relative reduction in SALT score, from Baseline at Week 24. The primary efficacy endpoint was met in both the 8 mg BID group and the 12 mg BID group. The difference between the 4 mg BID group and the placebo group was not statistically significant.

The primary efficacy endpoint result was supported by results of exploratory endpoints utilizing SALT as well as clinician-based assessments and patient reported outcomes. The 8 mg BID and 12 mg BID groups differentiated from placebo on various SALT analyses and had significant improvements in alopecia areata as measured by the CGI-I and PGI-I compared with the placebo group.

The improvements in alopecia areata symptoms observed in the CTP-543 treatment groups were progressive over time through 24 weeks and appeared to be dose responsive. Significant differences from placebo were noted as early as 12 weeks into treatment.

CTP-543 was generally well tolerated in all Cohorts.

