#### **Other Efficacy Endpoints**

For proportions of patients achieving specified improvement criteria (eg, CGI-I and PGI-I responders), pairwise treatment group differences from placebo at each scheduled evaluation will be assessed with the Cochran-Mantel-Haenszel test using baseline scalp hair loss as the stratification factor.

Absolute and/or relative changes in SALT score, SPRO score, CGI-S and PGI-S values, BELA and BETA score, QPRO scores, and HADS anxiety and depression scores, will be assessed with a mixed effects repeated measures (MMRM) model. The model will include fixed factors for treatment group, study visit, and treatment by study visit interaction, with baseline SALT score as a covariate. Treatment group comparisons at each visit will be based on least squares mean estimates. An unstructured covariance structure will be used to model the within-subject errors. The Kenward-Roger approximation will be used to estimate denominator degrees of freedom.

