# 7.2. Randomization

Approximately 440 patients are planned to be randomized in the study. Patients will be randomized in a 1:2:1 ratio (12 mg BID:8 mg BID:placebo) to each of three study arms:

- CTP-543 12 mg BID
- CTP-543 8 mg BID
- Placebo BID

Randomization will be stratified by scalp hair loss into one of the following two categories: 1) Partial scalp hair loss (SALT  $\geq$  50 and < 95); 2) Complete or near-complete scalp hair loss (SALT  $\geq$  95). The randomization schedule will be generated prior to study start.

All study patients, Investigators, and site study staff will be blinded to study drug assignment for the duration of the study. Tablets and packaging of CTP-543 and placebo will be identical in appearance.

A by-patient listing of randomized treatment group and randomization number will be presented.

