#### 8.2.2. Primary Analysis of the Primary Endpoint

Pairwise treatment group differences from placebo will be assessed with the Mantel-Haenszel test (common risk difference) using baseline scalp hair loss (partial vs complete/near-complete) as the stratification factor, for each active treatment group versus placebo.

For each imputed dataset, treatment differences will be assessed using the Mantel-Haenszel estimate of a common risk difference, with the variance estimator (used to construct confidence limits for the Mantel-Haenszel estimate of the common risk difference in the SAS FREQ Procedure). The resulting 100 estimates of the treatment differences and standard errors will then be combined using SAS PROC MIANALYZE. The following SAS options for PROC FREQ will be used to estimate a common risk difference, confidence intervals, and p-values by imputation for placebo compared to each dose separately:

proc freq data = <>;
by IMPUTATION;
tables STRATA\*TREATMENT\*RESPONSE / commonriskdiff(cl=mh test=mh);
run;

The observed number and percentage of patients with an absolute SALT score  $\leq 20$  among nonimputed data will be reported by treatment group along with the appropriate p-value, the combined treatment differences, combined standard errors, and 95% confidence intervals (CI). This analysis will be completed for the Efficacy Population and the Per Protocol Population. The analysis utilizing the Per Protocol Population is considered supportive. The results may also be displayed graphically.

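### The MMRM for relative change in SALT fits one baseline slope for all visits and omits the randomisation stratum, so its Week 24 standard error is probably conservative by about 1 to 9%

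*SAP*

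**What the plan says.** SAP 8.4.1 states that "relative change in SALT score from baseline at Weeks 4, 8, 12, 16, 20, and 24 will be assessed with a MMRM". Its mean model is: "The model will include fixed factors for treatment group, study visit, and treatment by study visit interaction, with baseline SALT score as a covariate". Protocol 12.4.2 (Other Efficacy Endpoints) has the same form, "with baseline SALT score as a covariate". SAP 8.4 adds: "An unstructured covariance matrix will be used to model the within-subject errors", with an autoregressive structure as the fallback if the model does not converge.

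On the stratum, SAP 7.2 says: "Randomization will be stratified by scalp hair loss into one of the following two categories", cut at a SALT score of 95. The primary analysis in SAP 8.2.2 is done "using baseline scalp hair loss (partial vs complete/near-complete) as the stratification factor, for each active treatment group versus placebo". The responder tests in SAP 8.4 and the log-rank test in SAP 8.5 are stratified too. No MMRM contains the stratum. The MMRMs for SPRO, CGI-S, PGI-S, BETA, BELA and QPRO have the same form, each with its own baseline score added. HADS, measured once after baseline, has an ANCOVA.

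On status, SAP 8.4 says: "All statistical tests outside of the hierarchy defined in Section 8.1.4 and Section 8.3 will be carried out at a two-sided significance level of" 0.05, with nominal p-values.

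**The concern.** Protocol 4.4.2 describes improvement in Phase 2 as "progressive over time through 24 weeks and appeared to be dose responsive". If that recurs, relative change varies little at Week 4 and a great deal at Week 24, and the influence of baseline severity grows over the same period. One slope cannot follow this. Under an unstructured covariance the slope is weighted towards the precise early visits, so it settles near their small value. Week 24 is then left with most of its baseline-related variance in the residual.

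At stake is the reported precision of the Week 24 LS mean differences and their 95% confidence intervals. Randomisation has already balanced the strata, but the model may not credit that balance.

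**Working it through.** **1. The plan's own figures.** The only precision figures are the powers for the primary endpoint in Protocol 12.1: about 92% for 8 mg and above 99% for 12 mg. With power = Φ((d − c − z·s0)/s1), c = 0.5(1/n1 + 1/n2) and z = 2.241 for two-sided 0.025:

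- 8 mg versus placebo: d = 0.26 − 0.09 = 0.17; c = 0.5(1/220 + 1/110) = 0.0068; pooled rate 67.1/330 = 0.203, so s0 = 0.0470; s1 = 0.0402.
- (0.17 − 0.0068 − 2.241 × 0.0470)/0.0402 = 1.44, giving 92.5%. The same formula gives 99.9% for 12 mg.

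Both figures reproduce. They fix the arm sizes (110/220/110) but say nothing about the MMRM.

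**2. Assumptions, none of them in the documents.** Share with SALT ≥95: p = 0.56. Residual SD: about 8 at Week 4 rising to 36 at Week 24. Autoregressive visit correlation: 0.75 to 0.9. Difference between strata at Week 24: Δ = 10, 20 or 30 points. Complete data.

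**3. Which visits set the slope.** The common slope is b = 1′S⁻¹β / 1′S⁻¹1. Here β holds the visit-specific slopes, and S is the residual covariance including the misfit from forcing one slope. Take Weeks 4 and 24 alone, with SDs 8 and 36 and correlation 0.85⁵ = 0.444. Leaving the misfit term out, the weight on Week 24 is

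(σ₁² − ρσ₁σ₂)/(σ₁² + σ₂² − 2ρσ₁σ₂) = (64 − 127.8)/(1360 − 255.6) = −0.06.

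With equal SDs it would be 0.5. With all six visits the common slope is about 0, against a Week 24 slope of 0.26 to 0.79. The share of the Week 24 slope recovered depends on how the SD grows:

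| SD from Week 4 to Week 24 | share recovered |
|---|---|
| 8 to 38 | −7% to 22% |
| 20 to 38 | −15% to 65% |
| constant | 58% to 100% |

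**4. Cost in standard error, by hand.** If adjustment does nothing at Week 24, the variance is 36² + p(1 − p)Δ² instead of 36². For 12 mg versus placebo, multiply the SD by √(2/110) = 0.1348:

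| Δ | p(1 − p)Δ² | SE, no help from baseline | SE, stratum difference removed | ratio |
|---|---|---|---|---|
| 10 | 24.6 | 4.90 | 4.85 | 1.01 |
| 20 | 98.6 | 5.04 | 4.85 | 1.04 |
| 30 | 221.8 | 5.25 | 4.85 | 1.08 |

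**5. Simulation.** Set A: 440 patients randomised 1:2:1 within stratum, 1,500 runs, correlation 0.75 or 0.9, stratum difference in the placebo arm set at 40% of that in the active arms. Set B: 60,000 patients scaled to 440, correlation 0.85. Model SE at Week 24, 12 mg versus placebo:

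| Set, Δ | no covariate | as planned | + baseline × visit | + stratum × visit | planned / full |
|---|---|---|---|---|---|
| A, 10 | 4.89 | 4.89 | 4.87 | 4.86 | 1.006 |
| A, 20 | 4.99 | 4.98–5.00 | 4.90 | 4.86–4.87 | 1.024–1.026 |
| A, 30 | 5.17 | 5.15–5.18 | 4.97 | 4.88–4.89 | 1.055–1.060 |
| B, 10 | 4.89 | 4.90 | 4.86 | 4.85 | 1.01 |
| B, 20 | 5.03 | 5.03 | 4.90 | 4.85 | 1.04 |
| B, 30 | 5.27 | 5.28 | 4.99 | 4.86 | 1.09 |

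In both sets the planned SE is within about 0.4% of the SE with no covariate.

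**6. Reported versus actual variability.** In set A (Δ = 30, correlation 0.9) the planned model reports 5.18, while its estimates vary across runs with SD 4.93. The full model reports 4.89 and varies by 4.93. Stratified randomisation has already delivered the precision; the planned model does not report it. Every model averages about −45 for a true −45.

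**7. Stronger association.** If baseline gives no help, the SE ratio is 1/√(1 − r²): 1.005, 1.02, 1.05 and 1.15 at r = 0.1, 0.2, 0.3 and 0.5. Solving the six-visit formula at r = 0.5 gives 1.10 to 1.18.

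**The case against.** The case against is substantial.

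- **The size is conditional.** It rests on SDs, correlations and slopes that the plan does not give. With a constant SD, the excess due to the common slope is about 2% or less. This stands, and it is why only a range can be given. A reader might infer that the Week 24 comparison is in effect unadjusted and its SE more than 10% too large. The documents do not support that as a fact: the first part needs strongly growing variance, the second a baseline-outcome correlation near 0.5.
- **The stratum is baseline SALT cut at 95, and baseline SALT is already in the model.** This largely stands. Once baseline by visit is included, adding the stratum lowers the SE by 0.1 to 1.7% in set A and by up to 2.6% in set B (4.99 to 4.86). In set A the missing visit interaction accounts for most of the loss.
- **Little turns on it.** The endpoint is nominal and outside the hierarchy, and the primary and key secondary analyses are stratified. At the simulated 45-point difference, z is 45/5.18 = 8.7 or 45/4.89 = 9.2. Only a small effect would feel it: for an assumed 12-point difference (correlation 0.9), approximate power at 0.05 is 69.0% versus 69.5% at Δ = 10, and 64.0% versus 69.0% at Δ = 30.
- **A common slope is a legitimate prespecified model, and extra terms can hinder convergence.** True, but the better-fitting form costs little.

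Two further readings go too far. One is that the treatment estimate is biased: with complete data it is not. An illustrative run with heavy assumed dropout (30% of near-complete placebo patients, 5% of partial placebo patients, 10% of active patients) gave −44.0 and −43.6 at Δ = 20 and 30, against a true −45; the full model gave −45.1 and −45.3 (Monte Carlo SE about 0.4). The documents give no dropout rates by arm and stratum, so this is no more than a caution. The other is that the HADS ANCOVA shares the fault: it has a single visit, so the slope mechanism cannot arise.

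**Conclusion.** The concern holds as a modest loss of reported precision. The planned model has one baseline SALT slope and no stratum. Given the progressive response seen in Phase 2, that slope is likely to be driven by the early visits, so the Week 24 SE for relative change in SALT is likely to be conservative. Under the assumptions in step 2 the excess is about 1 to 9%. It falls to about 2% or less from the common slope if the SD is constant over visits, and reaches 10 to 18% only with a baseline-outcome correlation near 0.5. The models that start at Week 12 lack the low-variance early visits; the expected excess there is about 0.5 to 4%. With complete data there is no bias, the error does not favour the drug, and no alpha-controlled result is affected.

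**What to change.** In SAP 8.4.1, add baseline SALT by visit to the relative-change MMRM, and add the randomisation stratum, by visit if the model converges. State the order of simplification: reduce stratum by visit to a stratum main effect before moving to the autoregressive covariance. For consistency, the same terms, with baseline outcome by visit, can go into the MMRMs that start at Week 12, where the expected gain is smaller. The slope argument gives no reason to change the HADS ANCOVA. Record the change in SAP section 13. If the database is already locked, report the fuller model as an additional analysis labelled as unplanned, as SAP 8.1.3 provides.

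Cost: with six visits, baseline by visit adds five parameters and stratum by visit six, 11 in all against about 440 patients. Baseline SALT and the stratum are partly collinear, so their own coefficients will be imprecise, but those are not of interest. No new data are needed.
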